10.3 ESTIMATED TOTAL BLOOD VOLUME

The estimated Total Blood Volume (TBV) will depend on age and gender and will be calculated with following formula:

Total Blood Volume = Weight * Average Blood Volume

Table 10.3.1:Approximate (average) blood volume per age category.

Age category	Approximate (average) blood volume (mL/Kg)
Term newborn infant	80 - 90 (85)
Infants	80
Children (> 3 months)	70-80
Adolescents	
women	65
men	75

For children the approximate total blood volume may vary between 70 - 80 mL/Kg. In order to be conservative, 70 mL/Kg will be used to calculate the total blood volume (TBV).

Examples of TBV calculations:

Infant of 1.5 year old, weight 10 Kg:

- Allowed blood loss at any single time (1% of TBV): 8 mL
- Allowed blood loss over four weeks (3% of TBV): 24 mL

Child of 12 years old, weight 45 Kg:

- Allowed blood loss at any single time (1% of TBV): 31.5 mL
- Allowed blood loss over four weeks (3% of TBV): 94.5 mL

Adolescent (male) of 15 years old, weight 60 Kg:

- Allowed blood loss at any single time (1% of TBV): 45 mL
- Allowed blood loss over four weeks (3% of TBV): 135 mL

Blood sampling could be withheld or reduced per Investigator's judgement, e.g. if limited by blood volume, bleeding and/or distress considerations especially in very young children.

If blood sampling is reduced, central lab parameters will be analysed in a priority order as indicated below:

- 1) Sum dabigatran pre-dose (baseline)
- 2) All coagulation biomarkers pre-dose, 30 minutes and 24 hours post-dose
- 3) Idarucizumab ADA pre-dose and 30 days post-dose
- 4) PK idarucizumab at time points pre-dose; 30 minutes and 24 hours post-dose
- 5) All coagulation biomarkers at time points prior vial 2, 4 hours and 12 hours post-dose
- 6) PK idarucizumab at time points prior vial 2, 4 hours and 12 hours post-dose

Boehringer Ingelhein	1	4 February 2016
BI Trial No.: 1321.7		
c08884404-01	Trial Protocol	Page 73 of 77
D		0.1. 0011 1

7) Unbound sum dabigatran at all time points as noted in Flow Chart

In below tables a few scenarios are displayed if collected blood volumes are limited.

Table 10.3: 1Reduced blood draw schedule (patients < 6 years of age):
Maximal 29 mL central lab/local safety blood draw (e.g. no EDTA blood
collection prior vial 2, 4 hours and 12 hours post-dose; i.e. no measurement of
unbound sum dabigatran and no PK idarucizumab prior vial 2, 4 hours and 12
hours post-dose)

		Time	EDTA	Na Citrate	Local Safety Lab	Total blood volume
Visit 1	1	Screening	11111		$\sim 2 \text{ to } 6 \text{ mL}$	~ 2 to 6 mL
Visit 2.1	2	Baseline (just prior vial 1)	2.7 mL	1.4 mL		4.1 mL
		Admini	ster Idaruciz	zumab Vial	1	
Visit 2.2	3	Just prior vial 2		1.4 mL		1.4 mL
	•	Admini	ster Idaruciz	zumab Vial	2	
Visit 2.2	4	30 minutes $(\pm 10 \text{ minutes})$	2.7 mL	1.4 mL		4.1 mL
	5	4 hours (± 30 minutes)		1.4 mL		1.4 mL
	6	12 hours (± 1 hour)		1.4 mL		1.4 mL
Visit 3	7	$\begin{array}{c} 24 \text{ hours} \\ (\pm 2 \text{ hours}) \end{array}$	2.7 mL	1.4 mL	~ 2 to 6 mL	~ 6 to 10 mL
Visit 4	8	Day 7 (± 3 days)				
Visit 5	9	Day 30 (+ 7 days)	1.2 mL			1.2 mL
Total blood	Total blood volume					~21 to 29 mL

Boehringer Ingelheim		4 February 2016
BI Trial No.: 1321.7		
c08884404-01	Trial Protocol	Page 74 of 77
		C' CC'1' 1 '

Table 10.3: 2Reduced blood draw schedule (patients < 6 years of age):	Maximal **25 mL** central lab/local safety blood draw (e.g. no blood collection prior vial 2, 4 hours and 12 hours post-dose; i.e. no measurement of biomarkers, unbound sum dabigatran and no PK idarucizumab prior vial 2, 4 hours and 12 hours post-dose)

		Time	EDTA	Na Citrate	Local Safety Lab	Total blood volume
Visit 1	1	Screening			~ 2 to 6 mL	~ 2 to 6 mL
Visit 2.1	2	Baseline (just prior vial 1)	2.7 mL	1.4 mL		4.1 mL
		Admini	ster Idaruciz	zumab Vial	1	
Visit 2.2	3	Just prior vial 2				
		Admini	ster Idaruciz	zumab Vial	2	
Visit 2.2	4	30 minutes (± 10 minutes)	2.7 mL	1.4 mL		4.1 mL
	5	4 hours (± 30 minutes)				
	6	12 hours $(\pm 1 \text{ hour})$				
Visit 3	7	$\begin{array}{c} 24 \text{ hours} \\ (\pm 2 \text{ hours}) \end{array}$	2.7 mL	1.4 mL	~ 2 to 6 mL	~ 6 to 10 mL
Visit 4	8	Day 7 (± 3 days)				
Visit 5	9	Day 30 (+ 7 days)	1.2 mL			1.2 mL
Total blood volume					~17 to 25 mL	

Boehringer Ingelheim		4 February 2016
BI Trial No.: 1321.7		
c08884404-01	Trial Protocol	Page 75 of 77
		C'1 CC1' 1 1

Table 10.3: 3 Reduced blood draw schedule (patients \geq 6 years of age):

Maximal **40 mL** central lab/local safety blood draw (e.g. no EDTA blood collection prior vial 2, 4 hours and 12 hours post-dose; i.e. no measurement of unbound sum dabigatran and no PK idarucizumab prior vial 2, 4 hours and 12 hours post-dose)

		Time	EDTA	Na Citrate	Local Safety Lab	Total blood volume
Visit 1	1	Screening			~ 3 to 6 mL	~ 3 to 6 mL
Visit 2.1	2	Baseline (just prior vial 1)	3.0 mL	2.7 mL		5.7 mL
		Admini	ster Idaruciz	umab Vial 1	l	
Visit 2.2	3	Just prior vial 2		2.7 mL		2.7 mL
		Admini	ster Idaruciz	zumab Vial 2	2	
Visit 2.2	4	30 minutes (± 10 minutes)	3.0 mL	2.7 mL		5.7 mL
	5	4 hours (± 30 minutes)		2.7 mL		2.7 mL
	6	12 hours (± 1 hour)		2.7 mL		2.7 mL
Visit 3	7	24 hours (± 2 hours)	3.0 mL	2.7 mL	~ 3 to 6 mL	~ 9 to 12 mL
Visit 4	8	Day 7 (± 3 days)				
Visit 5	9	Day 30 (+ 7 days)	3.0 mL			3.0 mL
Total blood	Total blood volume					~ 34 to 40 mL

Boehringer Ingelheim		4 February 2016
BI Trial No.: 1321.7		
c08884404-01	Trial Protocol	Page 76 of 77
		C'4 CC1' 4 1

Table 10.3: 4 Reduced blood draw schedule (patients \geq 6 years of age):

Maximal **32 mL** central lab/local safety blood draw (e.g. no blood collection prior vial 2, 4 hours and 12 hours post-dose; i.e. no measurement of biomarkers, unbound sum dabigatran and no PK idarucizumab prior vial 2, 4 hours and 12 hours post-dose)

		Time	EDTA	Na Citrate	Local Safety Lab	Total blood volume
Visit 1	1	Screening			~ 3 to 6 mL	~ 3 to 6 mL
Visit 2.1	2	Baseline (just prior vial 1)	3.0 mL	2.7 mL		5.7 mL
		Admini	ster Idaruciz	zumab Vial 1	l	
Visit 2.2	3	Just prior vial 2				
		Admini	ster Idaruciz	zumab Vial 2	2	
Visit 2.2	4	30 minutes (± 10 minutes)	3.0 mL	2.7 mL		5.7 mL
	5	4 hours (± 30 minutes)				
	6	12 hours (± 1 hour)				
Visit 3	7	24 hours $(\pm 2 \text{ hours})$	3.0 mL	2.7 mL	~ 3 to 6 mL	~ 9 to 12 mL
Visit 4	8	Day 7 (± 3 days)				
Visit 5	9	Day 30 (+ 7 days)	3.0 mL			3.0 mL
Total blood v	Total blood volume					~26 to 32 mL

Page 77 of 77

Proprietary confidential information © 2016 Boehringer Ingelheim International GmbH or one or more of its affiliated companies

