Adverse Events	X	Х	Х	Х	Х	Х
Concomitant therapies	X	X	Х	Х	Х	Х
Re-start anticoagulant therapy ¹⁰ (if applicable)				(X)		
Conclusion of patient participation ¹¹						Х

Boehringer Ingelheim		4 February 2016
BI Trial No.: 1321.7		
c08884404-01	Trial Protocol	Page 6 of 77

¹ Due to the need for urgent care in these patients, it is anticipated that the majority of screening procedures will have already been performed as part of the hospitalisation and diagnosis procedures. These procedures should not be repeated for the purpose of the trial. Any trial procedures that were not performed as part of routine care must only be performed after informed consent has been obtained.

Collection of medical history and other standard of care information up to the time of consenting must be provided as source documents as part of the study screening procedures and will be collected on the eCRF.

- ² The informed consent (and if applicable assent) should be obtained per local legislations and guidelines from the patient and/or the patient's legally accepted representative where applicable before any trial procedures are performed.
- ³ Blood pressure and heart rate will be measured approximately hourly while the patient is in the emergency or similar department, then approximately every 6 to 8 hours for the next 72 hours or until discharge, whichever comes first.
- ⁴ Bleeding severity for the index bleed (Group A) or any unusual bleed associated with surgery (Group B). Bleeding assessments during Treatment Period should be done at or near times of blood draws. The definitions for bleeding are based on recommendations made by the Perinatal and Paediatric Haemostasis Subcommittee during the 56th-58th Scientific and Standardization Committee (SSC) Meetings of the ISTH (R11-4225), refer to section 5.3.5.
- ⁵ Group B patients only (refer to section 3.3.1). Surgery/procedure assessments during Treatment Period should be done at or near times of blood draws.
- ⁶ Actual times for the start and end of the dosing of idarucizumab is to be recorded.
- ⁷ Refer to appendix 10.2 for detailed blood draw schedules. The pre-dose lab assessment is the baseline lab assessment.

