5.3.3 Safety laboratory parameters

Safety laboratory parameters will be performed by the local laboratories of the trial centres as noted in Flow Chart. Standard safety lab panel may include when feasible, the following measurements:

Page 40 of 77

Proprietary confidential information © 2016 Boehringer Ingelheim International GmbH or one or more of its affiliated companies

Haematology:

Red blood cell count, haemoglobin, haematocrit, white blood cell count and differential, platelets

Chemistry:

Glucose, albumin, total protein, sodium, potassium, chloride, urea, creatinine, alanine aminotransaminases (ALT), aspartate aminitransaminases (AST), alkaline phosphatase, total bilirubin or conjugated (direct)/unconjugated (indirect)

Pregnancy test (if applicable):

Local urine or other appropriate spot pregnancy test in female adolescents of child bearing potential (patients who have reached menarche) at time points as noted in the Flow Chart. More frequent testing can be done if required by the local regulation and/or authority or per Investigator's judgement. Enrolment of pregnant patients is not allowed.

Lab abnormalities:

Any local lab abnormalities should be followed-up per Investigator's judgement.

Blood sampling volume:

All efforts should be made to use the lowest amount of blood per sample as technically possible by using special paediatric collection systems. Blood sampling for this trial and for dabigatran trial 1160.106 or 1160.108 should not exceed the maximum blood volume limits recommended by the European Commission nor the maximum specified in local guidelines (if applicable), i.e. blood loss should not exceed 3% of the total blood volume (TBV) over four weeks and should not exceed 1% of the TBV at any single time (R10-4556; R10-4959).

Blood sampling could be withheld or reduced per Investigator's judgement, e.g. if limited by blood volume, bleeding and/or distress considerations especially in very young children.

Cross reporting of lab results might be applied (across studies 1160.106, 1160.108 and this trial) in order not to increase the blood volume required for analysis.

Refer to appendix 10.2 for further details of blood sampling.

Blood draws for pharmacokinetics, biomarkers, ADA can be found in section 5.4, section 5.5 and section 5.6. Refer also to the Flow Chart.

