All efforts should be made to use the lowest amount of blood per sample as technically possible by using special paediatric collection systems (R10-4556; R10-4959). Blood sampling for this trial and for dabigatran trial 1160.106 or 1160.108 should not exceed the maximum blood volume limits recommended by the European Commission (R10-4959) nor the maximum specified in local guidelines (if applicable), i.e. blood loss should not exceed 3% of the total blood volume (TBV) over four weeks and should not exceed 1% of the TBV at any single time.

Blood sampling could be withheld or reduced per Investigator's judgement, e.g. if limited by blood volume, bleeding and/or distress considerations especially in very young children. Refer to appendix 10.3 for several reduced blood draw schedules.

All invasive procedures in this trial must be performed only by qualified and experienced health care professionals/physicians with paediatric expertise, with limited attempts to draw blood and/or establish an intravenous (IV) line based on Investigator's judgement. Prior to venipuncture, a topical (percutaneous) analgesia to reduce pain associated with venipuncture, e.g. amethocaine gel or lidocaine-prilocaine (Emla) cream should be applied on the skin. This should be done according to standard paediatric procedures, and may be omitted only in patients who explicitly refuse it.

Boehringer Ingelheim BI Trial No.: 1321.7 c08884404-01

Trial Protocol

Page 70 of 77

Proprietary confidential information © 2016 Boehringer Ingelheim International GmbH or one or more of its affiliated companies

Table 10.2: 1

Blood draw schedule (patients < 6 years of age)

		Time	EDTA*	Na Citrate**	Local Safety Lab***	Total blood volume
Visit 1	1	Screening	/////	//////	$\sim 2 \text{ to } 6 \text{ mL}$	~ 2 to 6 mL
Visit 2.1	2	Baseline (just prior vial 1)	2.7 mL	1.4 mL		4.1 mL
		Adminis	ster Idaruciz	zumab Vial	1	
Visit 2.2	3	Just prior vial 2	2.7 mL	1.4 mL		4.1 mL
		Adminis	ster Idaruciz	zumab Vial 2	2	
Visit 2.2	4	30 minutes (± 10 minutes)	2.7 mL	1.4 mL		4.1 mL
	5	4 hours (± 30 minutes)	2.7 mL	1.4 mL		4.1 mL
	6	12 hours $(\pm 1 \text{ hour})$	2.7 mL	1.4 mL		4.1 mL
Visit 3	7	24 hours (± 2 hours)	2.7 mL	1.4 mL	~ 2 to 6 mL	~ 6 to 10 mL
Visit 4	8	Day 7 (± 3 days)				
Visit 5	9	Day 30 (+ 7 days)	1.2 mL	()))))		1.2 mL
Total blood	volur	ne				~29 to 37 mL

*EDTA K3 = PK assays, idarucizumab ADA

**Na Citrate = Biomarkers (dTT, ECT, aPTT, TT)

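### Protocol appendix 10.3: the Infants and Children blood-volume rows overlap, and the 1.5-year-old, 10 kg example is worked from the less protective row (8 and 24 mL, against 7 and 21 mL)

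*Protocol*

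**What the plan says.** Two limits govern sampling. Protocol 5.3.3 states that "blood loss should not exceed 3% of the total blood volume (TBV) over four weeks", and 10.2 adds that it "should not exceed 1% of the TBV at any single time". Both sections apply the limits to blood taken for this trial and for the parent dabigatran trial together.

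Appendix 10.3 supplies the total blood volume (TBV) that sites need to turn these percentages into millilitres. TBV is weight multiplied by an average volume per kg. The relevant rows of its table are:

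- Infants: 80 mL/kg, with no age range.
- "Children (> 3 months": 70-80 mL/kg.
- Adolescents: 65 mL/kg (female) and 75 mL/kg (male).

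On the range for children the text says: "In order to be conservative, 70 mL/Kg will be used to calculate the total blood volume (TBV". Three worked examples follow. The first is headed "Infant of 1.5 year old, weight 10 Kg" and gives 8 mL for a single time, then "Allowed blood loss over four weeks (3% of TBV): 24 mL". The others are a 12-year-old of 45 kg (31.5 and 94.5 mL) and a male adolescent of 15 years and 60 kg (45 and 135 mL).

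**The concern.** The only age cut printed beside these two rows is 3 months. A child of 18 months is well past it and so belongs in the children's row, where the protocol has chosen the cautious 70 mL/kg. The Infants row has no upper age, so the same child can also be placed there, at 80 mL/kg. The example takes the second route, which allows more blood to be drawn.

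The percentages in 5.3.3 and 10.2 do not settle which TBV to use; that is the job of appendix 10.3. A site with a toddler who may be bleeding could copy the example directly. Permission to reduce or withhold samples does not cure an unclear limit, because the investigator has to know the limit to decide when to reduce.

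**Working it through.** **Inputs.** TBV formula, volumes per kg and examples: appendix 10.3. Limits of 1% and 3%: sections 5.3.3 and 10.2. Tube volumes for patients under 6 years (2.7 mL EDTA, 1.4 mL citrate) and local safety draws of about 2 to 6 mL: Table 10.3: 1.

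**Step 1. Reproduce the printed figures.**

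- 1.5 years, 10 kg, at 80 mL/kg: TBV = 10 × 80 = 800 mL; 1% = 8 mL; 3% = 24 mL. This matches.
- 12 years, 45 kg, at 70 mL/kg: TBV = 3150 mL; 1% = 31.5 mL; 3% = 94.5 mL. This matches.
- Male, 15 years, 60 kg, at 75 mL/kg: TBV = 4500 mL; 1% = 45 mL; 3% = 135 mL. This matches.

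For the 10 kg child, 70, 75 and 85 mL/kg give 7 and 21, 7.5 and 22.5, and 8.5 and 25.5 mL. Of the values tried, only 80 mL/kg returns the printed pair.

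**Step 2. Apply the conservative children's basis.** TBV = 10 × 70 = 700 mL; 1% = 7 mL; 3% = 21 mL. Ratio: 24/21 = 8/7 = 1.143, so the printed limits are 14% higher. The gap is 1 mL per draw and 3 mL over four weeks at 10 kg.

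**Step 3. Can the choice change a decision?** Take Table 10.3: 1 at 10 kg. Assume local draws of 3 mL each (inside the printed range), no parent-trial blood, and Day 30 left out because it falls after four weeks.

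- Central samples: 4.1 + 1.4 + 4.1 + 1.4 + 1.4 + 4.1 = 16.5 mL.
- Two local draws: 2 × 3 = 6 mL. Four-week total = 22.5 mL.
- 24-hour draw: 2.7 + 1.4 + 3 = 7.1 mL.

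| | Volume | Infants basis (80) | Children's basis (70) |
|---|---|---|---|
| 24-hour draw | 7.1 mL | limit 8: pass | limit 7: fail |
| Four-week total | 22.5 mL | limit 24: pass | limit 21: fail |

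**Step 4. How far does this depend on the assumptions?** The four-week margin on the printed limit is 24 − 22.5 = 1.5 mL, so more than 1.5 mL of parent-trial blood would put the total above both limits. In the other direction, the Flow Chart footnote on screening says "it is anticipated that the majority of screening procedures will have already been performed". If the screening sample is routine care and not counted, the total is 22.5 − 3 = 19.5 mL, which meets both four-week limits, while the 7.1 mL draw still splits the two single-time limits. The illustration shows that the basis can matter; it does not fix the range over which it does.

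**The case against.** The strongest reply is that the appendix is consistent by label. The example is called an infant and uses the Infants row, the child uses 70 and the male adolescent uses 75. The conservative rule is stated for children, to settle a range, and the Infants row has a single value with no range to settle. The value 80 also lies within the printed range for children. All of that stands, so a reader who inferred a calculation error would be wrong.

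Nor do the documents define an infant for this table. The dosing text in 4.1.2 cuts both ways: it describes the lightest weight group as under one year, which does not fit an 18-month-old, but it also has a band of older infants from 6 to 10 kg, which fits a 10 kg patient. So 7 and 21 mL is the more cautious of two available readings, not the only possible one. What the reply does not remove is the overlap. If infants were meant to run past 18 months, the 3-month bound on the children's row would be wrong instead, and a line would still need changing.

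A reader might also infer that the protocol obliges sites to draw too much. It does not. The percentage limits govern, the reduced schedules are introduced with "In below tables a few scenarios are displayed if collected blood volumes are limited", any lower maximum in local guidelines applies, and the investigator may reduce or withhold samples.

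Finally, a reader might turn Step 3 into exact ranges of local draw volume for which the two bases disagree. Such ranges would hold only with no parent-trial blood, which the protocol requires to be counted.

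**Conclusion.** The point holds as an inconsistency in age categories that affects a paediatric safety limit. A 1.5-year-old of 10 kg fits two rows, and the worked limits come from the less protective one: 8 and 24 mL, against 7 and 21 mL on the basis that the protocol itself calls conservative, a 14% difference. The 7 and 21 mL figures rest on placing a patient past 3 months in the children's row. The claim that the choice can alter whether a schedule is allowed rests on the Step 3 assumptions.

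The practical reach is small. Section 7.7 plans about five patients, and section 3.2 expects the first to be 12 to 18 years old. Even so, section 3.3.2 admits patients from birth and section 3.2 sets no age staggering for this trial, so toddlers are eligible. No endpoint or analysis depends on the point. It is worth correcting because it concerns a limit that sites must work out for themselves and because the correction costs almost nothing.

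**What to change.** In appendix 10.3, end the Infants row at 3 months so that it meets the children's row without overlap. Relabel the 1.5-year-old example as a child, and print 7 mL (1%) and 21 mL (3%) for it.

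This changes a few lines and adds no samples, patients or analyses. The price is less blood for pharmacokinetic and coagulation samples in such children: at 10 kg, 1 mL less per draw and 3 mL less over four weeks, or about two 1.4 mL citrate tubes. The priority order already in appendix 10.3 says which central measurements to keep when volume is short.

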#### 2. LIST OF ABBREVIATIONS

Term	Definition / description
ADA	Antidrug antibodies
AE	Adverse event
AESI	Adverse events of special interest
ALQ	Above upper Limit of Quantification
ATC	Anatomical Therapeutic Chemical
aPTT	activated Partial Thromboplastin Time
BI	Boehringer Ingelheim
BLQ	Below lower Limit of Quantification
BRPM	Blinded report planning meeting
CRF	Case report form
СТР	Clinical Trial Protocol
CTR	Clinical Trial Report
dTT	diluted Thrombin Time
ECT	Ecarin Clotting Time
ICH	International Conference on Harmonisation
IPV	Important protocol violation
MedDRA	Medical Dictionary for Regulatory Activities
MQRM	Medical Quality Review Meeting
NOA	Not Analysed
NOR	No Valid Result
NOS	No Sample Available
PCC	Prothrombin Complex Concentrate
PD	Pharmacodynamics
PDS	Pharmacodynamic set
РК	Pharmacokinetics
РТ	Preferred term
REP	Residual Effect Period, after the last dose of medication with measurable drug levels or pharmacodynamic effects still likely to be present
SD	Standard deviation
SOC	System organ class
TBMA	Trial Biomarker Analyst
TCM	Trial Clinical Monitor

 TSAP for BI Trial No: 1321.7
 Page 5 of 20

 Proprietary confidential information © 2017 Boehringer Ingelheim International GmbH or one or more of its affiliated companies

Term	Definition / description	
ТСРК	Trial Clinical Pharmacokineticist	
TS	Treated set	
TSAP	Trial statistical analysis plan	
TSTAT	Trial statistician	
TT	Thrombin Time	
ULN	Upper Limit of Normal	
WHO	World Health Organization	

### **3. INTRODUCTION**

As per ICH E9 (1), the purpose of this document is to provide a more technical and detailed elaboration of the principal features of the analysis described in the protocol, and to include detailed procedures for executing the statistical analysis of the primary and secondary variables and other data.

This TSAP assumes familiarity with the Clinical Trial Protocol (CTP), including Protocol Amendments. In particular, the TSAP is based on the planned analysis specification as written in CTP Section 7 "Statistical Methods and Determination of Sample Size". Therefore, TSAP readers may consult the CTP for more background information on the study, e.g., on study objectives, study design and population, treatments, definition of measurements and variables, planning of sample size, randomisation."

SAS® Version 9.4 or higher will be used for all analyses.

### 4. CHANGES IN THE PLANNED ANALYSIS OF THE STUDY

Sample size is estimated to be approximately 5 patients. Depending on the actual sample size, listings only may be provided while the descriptive summaries specified in the protocol may not be displayed.

#### 5. ENDPOINTS

#### 5.1 **PRIMARY ENDPOINTS**

The primary endpoint is the safety of idarucizumab in a paediatric population as assessed by the occurrence of drug-related adverse events (including immune reactions) and all-cause mortality during the trial.

#### 5.2 SECONDARY ENDPOINTS

#### 5.2.1 Key secondary endpoints

This section is not applicable as no key secondary endpoint is defined.

#### 5.2.2 Other Secondary endpoints

- Percent change of coagulation tests (dTT and ECT) at 30 minutes post-dose compared to pre-dose.
- Time to achieve complete reversal of dabigatran effect, based on coagulation tests (dTT and ECT).
- Duration of complete reversal of dabigatran effect sustained at 24 hours post-dose, based on coagulation tests (dTT and ECT).
- Cessation of bleeding (Group A patients only).
- Bleeding status and other clinical conditions that may contribute to bleeding (Group A patients only) during the trial.
- Development of treatment-emergent ADA with cross reactivity to idarucizumab at 30 days post-dose of idarucizumab.

 TSAP for BI Trial No: 1321.7
 Page 9 of 20

 Proprietary confidential information © 2017 Boehringer Ingelheim International GmbH or one or more of its affiliated companies

